Comparison of Outcomes between the Use of Silverlon® Dressing and AQUACEL® AG dressing Post Cardiac Device Implant

Principal Investigator:

[name] FACC Director Center for Excellence in Atrial Fibrillation & Electrophysiology Research, Electrophysiologist, Professor, Department of Internal Medicine, University of Kansas Medical Center, Kansas City, KS 66160

Signature of PI:	Date:
------------------	-------

Co-investigators:

[name] MBBS [name] MD [name] MD [name] MD [name] MD [name] NP [name] MBBS [name] MD

Research and IRB site:

University of Kansas Medical Center Human Subjects Committee [name]

Study Sponsor: None.

Funded by: None.

Revised 22 January 2016

Protocol Summary

Silver impregnated dressings have been used widely since their introduction in the 1990s. A few studies have been done which showed that they may decrease the risk of post-operative infections of the wound sites. As a result of these studies there are several commercial available options, however we do not have any data on which ones are better. However, many aspects of the patient and the surgical wound may influence outcomes with respect to each dressing, one product may be more suitable for some patients. For example, given their lax skin texture, dressings with less adhesive may be better for elderly patients. This protocol describes our aim to prospectively study the two widely used dressings (namely Silverlon® and AQUACEL®AG) used at the University of Kansas Hospital for post-operative wound coverage and to assess which one has better patient outcomes.

Background

Implantation of cardiac implantable electronic devices has exploded in recent years. A nationwide analysis revealed that from 1997 through 2004, the number of pacemaker implants increased by 19% and that of automated implantable cardioverter defibrillators (AICDs) increased by 60% (1). Although cardiac implantable electronic devices (CIEDs) have made significant impacts in outcome of majority of implanted patients, these devices bought us a whole new set of problems due to both hardware issues and programing issues. Infections related to these devices have also increased from 5,308 in 2003 to 9,948 in 2011. The average mortality rate is 4.5% for patients with device infections which is high (2).

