- 3. To assess end points such as patient comfort at the time of removal (using a 1-10 pain scale), ease of removal (using a 1-5 scale completed by the operator), adherence of

the dressing at the post-op incision check 7 to 10 days post procedure (secondary outcome).

 To access skin breakdown and assigning a category/stage 1 – IV (using the National Pressure Ulcer Advisory Panel Pressure Ulcer States and Categories)

Design

This is a single-center, prospective, 2-arm randomized, non-blinded study involving about 200 patients total, 100 patient in the Silverlon arm and 100 patients in the AQUACEL® AG arm.

Location:

This study will be conducted at the University of Kansas Hospital, Kansas City, KS and Mid-America Cardiology locations.

Study inclusion and exclusion criteria

Inclusion:

- 1. All patients aged 18 or more who can give valid informed consent.
- 2. All patients who are scheduled for a CIED implant, generator change, upgrade at the University of Kansas Hospital.

Exclusion:

- 1. Patients who are already on antibiotics for another reasons.
- 2. Immunocompromised patients such as those on immunosuppressant's and HIV positive patients.
- 3. Patients who are post device explant for lead infection.
- Patients with an allergy to adhesive, silver or an allergy to the dressing(s) or their components.

Subject Enrollment

Potential subjects at the University of Kansas Hospital will be identified from daily EP procedure list. Subjects will be before their procedure or while in clinic for pre-op visit. All eligible patients will be offered to participate irrespective of sex, age, race, ethnicity or disability.

Subject Consent

Informed consent will be obtained from each patient. Participation in this study is voluntary and subject can decline at any stage. Participation in this study will have no impact on the patient's relationship with Mid America Cardiology or University of Kansas Hospitals or their associated facilities. After explaining the risks and benefits, informed consent will be obtained to participate in the study. They will be randomized into either Silverlon or AQUACEL® AG arm.

Randomization:

Block randomization will be used to permit uniform sample sizes at the end of our study. Randomization will be done with the aid of a computer based algorithm.

Intervention:

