Arm 1:Subjects randomized to this arm will receive Silverlon® dressing post operatively. Arm 2: Subjects randomized to this arm will receive AQUACEL® AG dressing post operatively.

Follow-Up:

No modifications are required for follow-up visits. All subjects will have their dressing evaluated in the cardiology office for an incision check at 7-10 days post procedure.

Photographs:

Photographs of the incision site will be taken immediately post-procedure and during the 7-10 days post procedure visit. Images of the incision site and the area immediately surrounding it will be visible. No identifying features of the patient will be visible in the photographs. The purpose of the photographs is to document the appearance of the skin surrounding the wound. Photographs will taken by the separate performing the incision check on a digital camera that is kept in a secure, locked cabinet when the camera is not in use. Images will be labeled with the subject number, stored electronically (.jpg, .png or other relevant format) and uploaded to the secure KUMC server. Photographs may be used for finitely.

Data Collection

The following variables will be collected by electronic medical record query or during the interview with the subject. Patient information will be coded with the following system: 001,002,003 etc.

Variables:

- 1. Demographics: Age, Sex, Race, Height, Weight, BMI.
- 2. Past Medical History: HTN, CAD, Thyroid status, OSA, DM, HLD, CVA, CKD, Valvular Diseases, Smoking History, COPD, CHF, peripheral vascular disease
- 3. Medication History: Antiplatelet agents, anticoagulants, steroids, hypoglycemic,
- 4. Indication for procedure.
- 5. Procedure notes.
- 6. Complications including post op hematoma
- 7. Discharge medications including antibiotics used for generator exchanges
- 8. Follow up post op Day 7 -10: Appearance of skin surrounding wound including grading of swelling (mild swelling compared to the contralateral side vs significant swelling), presence of any erythema (compared to skin on the contralateral side), patient comfort level (from 1-5). Incidence of frank infection and ease of dressing removal (from 1-5) by nurse practitioner, Skin laxity (firm skin vs lax skin which is prone to tearing), presence

or absence of leg edema (a surrogate indicator of subcutaneous edema at the wound site which would predispose to evisceration of skin at the time of dressing removal)

Statistical Considerations

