The primary efficacy outcome of the study is the prevention of infection. Secondary outcomes include the side-effects such as trauma at the time of removal, ease of removal and patient discomfort at the time of removal.

Standard statistical tools will be utilized. SPSS and STATA® version 9.0 will be used to analyze the data. Continuous data will be described as the mean value \pm SD, and categorical data will be described as frequencies. The association between a clinical event/ endpoint and specific clinical and laboratory variables will be evaluated using the t test for continuous variables or the Fischer exact test for categorical variables. A p value <0.05 will be considered statistically significant.

Confidentiality

The data will be collected on data sheets and will be stored in a locked cabinet. This data will be transferred to an access database within the KUMC Cardiovascular Research Institute, which has a secure password protected main frame. Once all the data is analyzed, the data will be deleted and the paper records will be shredded.

Study Records

All records relative to the research will be treated in confidence and stored in the CVRI Department. The records will be available only to the investigators and any agents of the University or federal government who oversee research involving human subjects.

Safety Monitoring

All incidences of serious adverse events observed will be reported to the principal investigator. These events will be reviewed against the HSC reporting criteria; all events meeting the reporting criteria will be forwarded to the HSC.

Risks, Benefits and Justification of the Research Study

Risks:

There are no additional risks for patients that participate in this study. Each of the patients would have received one of the two dressings even if they were not part of this study.

Benefits:

This study will help in identifying new methods of improving the efficacy and outcomes of the dressings used for CIED patients at the University of Kansas Hospital.

References

2. HCUPnet. Healthcare Cost and Utilization Project (HCUP). 2006-2009. Agency for Healthcare Research and Quality, Rockville, MD. http://hcupnet.ahrq.gov/ Accessed 2014.

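### No test is assigned to the dressing comparison and no covariate adjustment is planned; adjusting the secondary removal scores for age could add some precision at almost no cost

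*Combined protocol and SAP*

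**What the plan says.** **Analysis.** The Statistical Considerations section contains the whole analysis plan. Its one sentence on inferential methods has as its subject how endpoints relate to clinical and laboratory variables, and says that this "will be evaluated using the t test for continuous variables". It continues with the Fisher exact test for categorical variables. The threshold follows: "A p value <0.05 will be considered statistically significant". No regression, ANCOVA, stratified analysis or list of covariates appears in the document.

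**Design.** The Design section plans about 200 patients, "100 patient in the Silverlon arm and 100 patients in the AQUACEL® AG arm". On allocation, the Randomization section says "Block randomization will be used to permit uniform sample sizes at the end of our study". It mentions no stratification by age or skin condition.

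**Patient factors.** The Protocol Summary says that features of the patient and the wound may affect how each dressing performs, and gives an example: "given their lax skin texture, dressings with less adhesive may be better for elderly patients". Data Collection, item 1, lists "Demographics: Age, Sex, Race, Height, Weight, BMI". Diabetes and steroids appear in items 2 and 3. Skin laxity, leg edema and swelling appear only in item 8, the day 7-10 follow-up.

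**Removal scores.** The Objectives list "ease of removal (using a 1-5 scale completed by the operator" and patient comfort on a 1-10 pain scale, both as secondary outcomes. Data Collection, item 8, records patient comfort from 1 to 5.

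**The concern.** The protocol suggests that patient characteristics may matter to dressing outcomes and collects age, but gives it no stated role in comparing the dressings, either through stratified randomisation or through the analysis. If age predicts discomfort or ease of removal, an unadjusted comparison leaves that variation in the error term. It also leaves the estimate uncorrected for whatever age difference arises by chance between the arms.

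At stake is the precision of two secondary comparisons. Pre-specification matters as well: the study is not blinded and many candidate covariates are collected, so adjusters chosen after the results are seen would be open to selection.

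**Working it through.** **Inputs from the documents:** 100 per arm; significance at p < 0.05 (sidedness not stated, taken as two-sided).

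**Assumed inputs:** a true difference of 0.35 SD; scores treated as continuous; baseline variables explaining a fraction R² of the score variance, from 1% to 20%. The documents give no SD, target difference, power or correlation.

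**The plan's own figure.** The 200 patients come with no derivation, so there is nothing to reproduce. For orientation, the difference detectable with 80% power by an unadjusted test is (1.960 + 0.842) × √(2/100) = 0.396 SD.

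**Effect of adjustment.** Regression on baseline variables shrinks the residual SD by √(1 − R²), so the standardised difference becomes 0.35/√(1 − R²). The non-centrality parameter is that value × √(100/2). Power comes from the non-central t distribution with 198 degrees of freedom (critical value 1.972). The degree of freedom spent on one covariate is negligible. The equivalent unadjusted total is 200/(1 − R²).

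| R² | Standardised difference | Non-centrality | Power | Equivalent total N |
|---|---|---|---|---|
| 0 | 0.350 | 2.475 | 69.2% | 200 |
| 1% | 0.352 | 2.487 | 69.7% | 202 |
| 4% | 0.357 | 2.526 | 71.0% | 208 |
| 5% | 0.359 | 2.539 | 71.5% | 211 |
| 10% | 0.369 | 2.609 | 73.8% | 222 |
| 20% | 0.391 | 2.767 | 78.6% | 250 |

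Unrounded, the 5% row is 71.46%, hence 71% as a whole number. The gain is 0.5 points at R² = 1%, 1.8 at 4% and 9.4 at 20%.

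**Check by simulation.** With 4,000 trials per setting, one baseline covariate with correlation ρ to the score (R² = ρ²) and a true difference of 0.396 SD:

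| ρ | R² | t test | Adjusted |
|---|---|---|---|
| 0.1 | 1% | 78.2% | 78.8% |
| 0.3 | 9% | 81.4% | 84.6% |
| 0.5 | 25% | 79.7% | 89.8% |

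With no true difference, both methods rejected in 4.5% to 4.8% of trials. Both are valid, and only efficiency differs.

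**Chance imbalance.** The standard error of the age difference between arms is √(2/100) = 0.141 age SDs. A gap of 0.2 SD or more in either direction is 0.2/0.141 = 1.41 standard errors, which arises in about 16% of randomisations. A gap of 0.2 SD shifts the unadjusted estimate by 0.2 × ρ. If age alone explained 5% of the variance (ρ = √0.05 = 0.224), the shift is 0.045 SD; at 20% (ρ = 0.447) it is 0.089 SD.

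**The case against.** **The cited sentence does not concern the dressing comparison.** A reader might infer that the plan prescribes an unadjusted t test for Silverlon against AQUACEL AG. The sentence is about endpoints and clinical or laboratory variables, and no other sentence assigns a test to the arm comparison. This stands: what can be said is that the comparison is unspecified and that the only tests named are unadjusted.

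**The Protocol Summary does not name age as a driver of removal scores.** A reader might take it that way. Its wording is tentative, and its example concerns which dressing suits which patient, which is effect modification. The remarks on laxity and edema in Data Collection concern skin damage, not discomfort or ease. This also stands. A model with age as a main effect does not test whether the better dressing depends on age; that would need a separate pre-specified dressing-by-age term.

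**The other covariates have little support.** Nothing in the documents links BMI, diabetes or steroid use to these scores. The exclusion of patients on immunosuppressants may leave few steroid users. The two items tied to skin damage at removal are recorded at day 7-10, after assignment in an unblinded study, and are unsafe adjusters. That leaves age as the core term.

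**The gain may be negligible.** The effect size and every R² are assumed, and at R² of 4% or less the gain is under 2 points. This stands as to size. It does not remove the case for adjustment, because one pre-specified covariate costs one degree of freedom if it explains nothing.

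**There is no validity problem.** A reader might infer bias from the lack of stratification. Randomisation balances age in expectation, and chance imbalance is already allowed for in the error rate of the unadjusted test.

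**Conclusion.** The point holds as a modest efficiency suggestion. The plan assigns no test to the dressing comparison, plans no covariate adjustment, and collects age without giving it a stated role in that comparison. If the removal scores were compared without adjustment, the result would be valid but possibly less precise than it could be.

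At an assumed 0.35 SD, the power forgone runs from half a point to about nine points as R² goes from 1% to 20%. Where this trial falls in that range cannot be told from the documents, so a material loss of precision is possible but not shown. The scores are secondary outcomes, and the primary outcome, infection, is not affected.

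**What to change.** In Statistical Considerations:

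1. State that discomfort and ease of removal will each be compared between arms by linear regression on dressing, with age (continuous) as the baseline covariate. Report the unadjusted test beside it.
2. Treat BMI, diabetes and steroid use as optional. Any that are included must be fixed before data are examined and taken from their values before the dressing is applied.
3. Do not adjust for items recorded at day 7-10 (skin laxity, leg edema, swelling) or for complications.
4. Leave the infection comparison unadjusted, since too few events are likely to support a model.
5. Reconcile the comfort scale, which is 1-10 in the Objectives and 1-5 in Data Collection, so that the dependent variable is defined.

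The cost is a few lines of text and one correction to the scale. Age is already collected, and no patients or visits are added.
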